The potential for pharmacologically-induced stress to produce observable wall abnormalities (WMA) is well documented in the echocardiography literature (4, 7-9). The mechanism for inotropic agents (dobutamine) to induce wall motion abnormalities is to increase oxygen demand by increasing heart rate and the force of contraction (10). In contrast, dipyridamole and other vasodilators effectively reduce the supply of oxygen available to myocardial segments served by diseased coronaries, with the sub-endocardium being particularly vulnerable (11). A limitation of dipyridamole echocardiography is that the recommended dosages are considerably higher than for nuclear myocardial perfusion scintigraphy (0.84 mg/kg over 10 minutes vs. 0.56 mg/kg over 4 minutes respectively (12). In a study of 10,451 patients (10% with documented or suspected coronary disease), 1.2% of patients had a major adverse reaction (13) and 67% reported minor side effects (headache, flushing, gastrointestinal, 14). Further, dipyridamole stress alone is often insufficient and necessarily supplemented with atropine to improve test sensitivity.

Regadenoson functional imaging potentially offers a significant improvement in the side effect profile over high dosage dipyridamole without sacrificing sensitivity. Porter et.al (7) reported similar sensitivity to WMAs in the presence of CAD (61%) to dipyridamole (66% without atropine administration, 15) with no reported major side effects. Despite the comparable sensitivity, the absolute sensitivity is significantly less than perfusion based techniques.

Cardiac magnetic resonance (CMR) imaging is increasingly being used in the assessment of regional and global left ventricular function at rest and during vasodilator stress (16-18). CMR has many important technical advantages including a higher spatial resolution than PET or SPECT, improved tissue characterization (both with and without contrast), and superior repeatability and endocardial definition (including functional assessment) over echocardiography. Its power of tissue characterization is particularly highlighted with the use of late gadolinium enhancement (LGE) and its excellent spatial correlation with infarction, necrosis, and fibrosis (19). With respect to wall motion, myocardial strain imaging with CMR uses magnetic saturation "tag" lines (figure 1) to aid in qualifying and quantifying wall motion, is superior to echo-based strain techniques, and has been demonstrated to correlate well with LVEF (20-23).

At this time, there is ample evidence that vasodilator stress induces functional changes (4-7,9,11,12); however, without an understanding of the etiology of this process, its value in patient management is limited. In order to use functional changes induced by vasodilator stress, it is necessary to first understand the relationship between functional and perfusion abnormalities, local strain and fibrotic burden.

It is the intent of this research to quantify the effects of regadenoson on myocardial function and contraction in the presence of CAD. We are proposing a CMR protocol to evaluate myocardial viability and function, with CMR tagging, on a segment-based approach. We plan to evaluate correlations in wall motion changes (ie. - myocardial radial strain (ΔR) and/or displacement ($\Delta\theta$)) during regadenoson stress and correlate with areas of myocardial infarction (late gadolinium enhancement on CMR), areas with identified perfusion defect (on PET), and a change in LVEF magnitude (on both PET and CMR).

Figure 1: Tagged short axis cine view of the left ventricle (left panel) and late gadolinium enhancement image (right panel) showing a near transmural infarction of the septal wall.

HYPOTHESIS

The hypothesis of this study is that in a population with a demonstrated perfusion defect and WMA (measured by Rb-82 PET), regadenoson stimulates changes in ventricular mechanics (radial strain and rotational displacement) and LVEF associated with the degree of ischemic or fibrotic burden. Additionally, these changes may be different for normal, ischemic, and infarcted myocardium and will be compared between a high-risk population and a cohort of low-likelihood normals.

PRIMARY END-POINTS

For each patient group, every segment of the myocardium will be classified as normal, reversible, or non-reversible based on the PET perfusion data. Then for each segment category the radial strain (ΔR) and rotational displacement ($\Delta\theta$) will be calculated using an industry

standard CMR software package (current plans are to use HARP®, Diagnosoft, Morrisville, NC, though another package may be used). These values will be determined from tagged cine images obtained in three short axis (apical, mid, and basal) views of the left ventricle obtained during regadenoson induced stress and at rest (or difference in stress values).

1. Primary End-Point 1 of this study is to determine if there is a measurable difference in the strain (ΔR) and/or displacement ($\Delta\theta$) of normal and abnormal segments between the defined ischemic and normal patient groups.
2. Primary End-Point 2 of this study is to determine if there are measurable differences in the strain (ΔR) and/or displacement ($\Delta\theta$) between segment classifications (normal, reversible, and non-reversible perfusion defects).

SECONDARY END-POINTS

Secondary end-points will be determined from tagged cine images obtained in three short axes (apical, mid, and basal) views of the left ventricle obtained during regadenoson induced stress and at rest (or difference in stress values).

1. Secondary End-Point 1 of this study is to determine the strain (ΔR) and/or displacement ($\Delta\theta$) scores correlate with flow reserve as measured by PET and/or transmural extent of infarction (TEI) indicated by Late Gadolinium Enhancement (LGE).
2. Secondary End-Point 2 of this study is to track any adverse events as a result of participation in this study.

STUDY DESIGN

Subjects who have had a clinically indicated, ECG-gated, Rb-82 myocardial perfusion PET study will be recruited for participation. Specific inclusion/exclusion criteria are:

Inclusion Criteria

1. Myocardial rest/regadenoson stress perfusion PET study within 60 days
2. Rest LVEF (greater than or equal to 35%)
3. No change in symptoms or treatment between the PET and the MRI study
4. Willing to consent to the study
5. Male or female who is either post-menopausal, surgically sterile, or if has a childbearing potential, a negative pregnancy test within 2 days prior to the MRI study.
6. An estimated glomerular filtration rate completed within 6 months of participation.

Exclusion Criteria

1. Metallic implants, pacemaker, blood vessel clip (contra-indicated for MRI)
2. Patient size exceeds MRI bore/table limits: (Max body diameter > 70 cm, weight > 136 kg)
3. Second or third degree AV block
4. Sinus node dysfunction
5. Acute myocardial infarction (past 3 months)

6. Actively wheezing or with acute asthma or bronchospastic attacks requiring changes in therapy within the past 30 days
7. Patients that have experienced a previous hypersensitivity reaction thought to be related to regadenoson
8. Pregnant Women

STUDY PROCEDURES

Study staff will provide each subject with full and adequate verbal and written information using an IRB approved informed consent document, including the objective and procedures of the study and the possible risks involved before inclusion in the study. Informed consent will be obtained prior to performing any study-related procedures. If consent is gained, a copy of the executed consent form will be provided to the subject.

Following consent execution and prior to the MRI, the following screening measures will be performed and documented:

- Medical history, including surgeries and procedures;
- Medications, including herbal supplements and vitamins, will be reviewed;
- A MRI Patient Safety Screening questionnaire completed;
- Vital signs will be taken, to include heart rate, breathing rate, and blood pressure will be collected;
- An electrocardiogram will be performed;
- An intravenous catheter will be placed into the subject's arm;
- Females of child-bearing potential* will undergo a serum pregnancy test;
- If a creatinine blood test has not been done clinically in the last six months, one will be performed; and
- The qualifying, clinically-indicated cardiac PET procedure records will be collected.

** Females of childbearing potential are defined as not postmenopausal or surgically sterilized.*

Consented subjects will be asked to undergo a rest/Lexiscan® (Regadenoson) stress cardiac MRI examination. For patients who do not have an estimated glomerular filtration rate on record within 6 months of participation, a creatinine will be drawn as part of the screening procedures. Patients with renal dysfunction (defined as an estimated glomerular filtration rate (GFR) < 60 mL/min/1.73m² within 6 months of participation) or a history of gadolinium contrast allergy or intolerance will participate in an abridged non-contrast protocol consisting of the localizer, functional and stress imaging sequences only, and no contrast will be administered.

There will be 40 subjects recruited into this study. 15 subjects will be recruited who had normal perfusion, normal LVEF and no WMA on a clinically indicated cardiac PET study. 25 subjects will be recruited into the ischemic cohort. Consented study participants will receive one dose of Lexiscan® (Regadenoson) while taking part in this protocol.

Ischemic Patient Population

The abnormal population will be selected from a group of patients with a clinically indicated myocardial perfusion PET study demonstrating reversible ischemic perfusion defect, a rest LVEF of $\geq 35\%$, and demonstrated WMA by quantitation, utilizing QPET's QGS analysis program

(Cedars Sinai Health System, Los Angeles, CA). A WMA will be defined as having a drop in LVEF from rest to stress and/or an extent of greater than or equal to 10% thickening and/or motion.

Myocardial perfusion rest/Regadenoson PET protocol

All PET studies will have been clinically indicated and performed prior to study participation. These studies will have been performed on a Biograph™-16 or Biograph™-64 PET/CT or Siemens ACCEL Dedicated PET system (Siemens Medical Solutions, Erlangen, Germany).

Biograph™-16 or Biograph™-64 PET/CT System

A low-dose CT image acquisition will have been acquired for attenuation correction. The resting perfusion images will have been acquired using 20-40 mCi of Rubidium-82, infused over 35 seconds. The ECG gated, list mode acquisition will have started prior to the start of the rubidium-82 infusion and continued for 7 minutes.

With the subject in the same position, a single 0.4 mg dose of regadenoson in 5 mL saline will have been administered as a bolus over 10 seconds and immediately followed by a 5 mL saline flush. Following a 30 second delay, the stress images will have been acquired using 20-40 mCi of Rubidium-82 in ≤ 50 ml saline infused over <35 seconds. An ECG gated, list mode acquisition will have been started prior to the start of the Rb-82 infusion and continued for 7 minutes. A second low dose CT scan will have then been acquired for attenuation correction of the stress study.

Siemens ACCEL Dedicated PET

An infusion of 50 mCi of Rubidium-82 will be delivered 10 seconds after the beginning of the dynamic acquisition. First, a 150 second 2D dynamic acquisition will be acquired and followed by a 300 second 3D gated acquisition. Transition between 2D dynamic and the 3D gated acquisition was approximately 120 seconds.

With the subject in the same position, a single 0.4 mg dose of regadenoson in 5 mL saline will have been administered as a bolus over 10 seconds and immediately followed by a 5 mL saline flush. Following a 30 second delay, the stress images will have been acquired using 50 mCi of Rubidium-82 in ≤ 50 ml saline infused over <35 seconds. The 2D dynamic acquisition will have been followed by a 3D stress ECG gated acquisition.

Patients that meet these inclusion criteria will be discovered using a review of the St. Luke's nuclear database.

Cardiac MRI examination

All MRI studies will be conducted on either a 1.5-Tesla or 3.0 Tesla magnet. When subjects arrive, they will be consented and prepared for MRI scanning. The scanning technician will prepare the subject (screening, change of clothes, placement of positioning pillows, placement of hearing protection, vectorcardiogram leads, and an IV). Subjects will lie supine on the MRI table and then be advanced into the magnet bore. Of the subjects meeting inclusion/exclusion

criteria, those with a GFR < 60 mL/min/1.73m² or a history of gadolinium contrast allergy or intolerance will only perform the non-contrast portion of the following protocol, all others will follow the full protocol (Figure 2):

Non-Contrast CMR examination (Tagging at Rest, Stress)

- Localizers
- Pre-Contrast Rest Tagging Images:
 - Short Axis Cine (apex, mid, base)
 - Long Axis Cine (horizontal, vertical)
- Inject Regadenoson
- Pre-Contrast Stress Tagged:
 - Short Axis Cine (apex, mid, base)
 - Long Axis Cine (horizontal, vertical)
- Reverse Patient with aminophylline (if necessary)

*Late Gadolinium Enhancement to assess infarcted and fibrotic tissue:

- Injection of gadolinium contrast agent
- Delay of at least 8-15 minutes from injection
- Cine IR TI Scout
- LGE Short Axis(apex, mid, and base)
- LGE Long Axis(horizontal and vertical)

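### The primary variable is not fixed as the stress-minus-rest change, so a resting deficit could be reported as a primary finding without any test of regadenoson response

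*Combined protocol and SAP*

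**What the plan says.** The aim and hypothesis are about change. The background says "We plan to evaluate correlations in wall motion changes" under regadenoson. The Hypothesis section states that "regadenoson stimulates changes in ventricular mechanics" and that "these changes may be different for normal, ischemic, and infarcted myocardium". The Powering Calculation also starts from a difference in rest-to-stress change of ejection fraction between the groups.

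The primary variable is looser. Under Primary End-Points, strain and rotation come from tagged images "obtained during regadenoson induced stress and at rest (or difference in stress values"). The Primary End-Point Analysis repeats the choice almost word for word, and neither section defines the alternative in the parenthesis. End-Point 1 "is to determine if there is a measurable difference in the strain (ΔR) and/or displacement" between patient groups and names no state. In the analysis section, End-Point 2 compares abnormal with normal segments at rest and at stress. The only methods named are ANOVA and t-tests. No change score, adjustment for rest or interaction term is required.

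On recruitment, the normal group consists of subjects "who had normal perfusion, normal LVEF and no WMA" on PET. The general criterion is "Rest LVEF (greater than or equal to 35"%), and the Ischemic Patient Population section repeats that floor. A wall motion abnormality there may be met by an LVEF drop from rest to stress.

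**The concern.** Followed as written, the plan can yield a primary finding that says nothing about the drug. If ischemic patients or abnormal segments contract less at rest, and regadenoson changes all groups equally, strain will differ at rest, at stress or both. Each of those differences answers the endpoint as worded, but none answers the hypothesis.

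Reporting both states does not cure this. One significant and one non-significant comparison is not a test of the difference between them. By chance the stress test can reach significance while the rest test does not, and that pattern invites a drug-effect reading even when the change is identical.

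A resting difference is likely here. The cohorts are selected on different LVEF criteria, and non-reversible perfusion defects form one of the segment classes.

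A second opening lies in the and/or between strain and displacement. Either measure can carry either primary endpoint, with no ranking and no multiplicity rule.

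**Working it through.** **The plan's own figure.** The Powering Calculation adds an 8% rise in normals and a 2% change in ischemic patients to get 10%, which it converts to a 5.6% radius change. Dividing by the 5.3% SD of resting LVEF gives 5.6/5.3 = 1.057, the stated d of 1.06. With a two-sided 0.05 t-test (level and sidedness are not stated), power at d = 1.06 is 0.800 with 15 per group, 0.827 with the stated 16 and 0.837 with 13 versus 22. The stated sizes are therefore reproduced. The contrast sized is a difference in change, but the SD belongs to a single state. SD(change) = SD(state) × √(2(1 − ρ)), and the two are equal only at rest-stress correlation ρ = 0.5.

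**Inputs for the illustration.** The 13 and 22 evaluable patients come from the plan. The deficits, correlations and two-sided 0.05 level are assumptions, because the documents give none. Each patient contributes one value per state, SDs are equal, and the deficit is the same at rest and at stress, so the true difference in change is zero.

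**End-Point 1, 13 versus 22, ρ = 0.7** (20,000 simulated trials):

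| Deficit | Rest test | Stress test | Either | Both | Stress only | Change |
|---|---|---|---|---|---|---|
| 0.5 SD | 29% | 28% | 39% | 18% | 11% | 5% |
| 1 SD | 79% | 79% | 88% | 70% | 9% | 5% |

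Stress only is stress minus both: 0.283 − 0.176 = 0.107 and 0.794 − 0.704 = 0.090. The noncentral t distribution gives 0.284 and 0.792 for a single test, which agrees. As ρ goes from 0.3 to 0.9, the either column runs from 45% to 34% at 0.5 SD and from 93% to 84% at 1 SD. The change test stays at 5%.

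**End-Point 2, 22 ischemic patients, paired class means, ρ = 0.7, between-class correlation 0.5, deficit 0.5 SD.** Rest 61%, stress 61%, either 73%, change 5%. With between-class correlation 0.3 or 0.7, either is 60% or 90%.

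**Multiplicity.** Two endpoints × two measures = four tests. If they are independent, 1 − 0.95⁴ = 0.185 (0.187 simulated). The simulated family-wise error is 0.156 at correlation 0.5 and 0.115 at 0.8.

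**Selection on the LVEF drop.** Let the PET LVEF change be standard normal with mean 0. Normals are drawn from values ≥ 0 and ischemic patients from values < 0. The CMR change correlates r with the PET change, and there is no other group effect. The between-group change test is then significant in:

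| Ischemic patients entering by a drop | r = 0.3 | r = 0.5 | r = 0.7 |
|---|---|---|---|
| All | 28% | 68% | 96% |
| Half | 17% | 40% | 73% |

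The within-patient class contrast stays at about 5% if the drop is shared evenly across classes. It does not if the drop is concentrated in abnormal segments.

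**The case against.** **Change may well be intended.** The sample size starts from a difference in change, and the background sentence glosses wall motion changes as ΔR and/or Δθ under stress. The parenthesis can be read as loosely worded stress minus rest. This stands as evidence of intent, and it is the reason to write the intent down. It does not settle the text: the analysis section compares ΔR at rest and at stress, so the symbol denotes strain in a state, and the parenthesis is only an alternative.

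**The 39% to 88% is not an error rate.** It is the chance of detecting a real deficit that was built in, and the endpoints as worded ask for a difference in strain. That is right. The figures measure how easily a primary result can arise without any difference in response. The specific misreading, stress significant and rest not, is 11% to 9%, against about 3% with no deficit.

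**The 5% for the change test does not hold for End-Point 1 if selection on an LVEF drop matters.** This also stands. Those figures depend on the assumed mean PET change: a mean of +1.5 SD gives 43%, 87% and over 99% when all enter by a drop. It limits what End-Point 1 can show, but it does not justify leaving the variable open.

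**Four tests may be too few.** If rest and stress each count there are eight, with family-wise error of 16% (correlation 0.8) to 34% (independent). Four is therefore the conservative count.

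**Conclusion.** The concern holds. It rests on the wording: the hypothesis and the start of the sample-size argument concern change, while the primary analysis permits rest and stress values and makes any difference score optional and undefined. An ANOVA with a class-by-state interaction would be compatible with the text but is not required by it.

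The simulated percentages show scale only and depend on the stated assumptions. They also ignore clustering of segments within patients. The matter should be corrected before analysis. It does not prevent the trial from answering its question, because the data needed are collected.

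**What to change.** In both Primary End-Points and Primary End-Point Analysis:

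- Make the stress-minus-rest change, or equivalently the group-by-state or class-by-state interaction, the primary variable for both endpoints. Delete the parenthetical alternative and report rest and stress values descriptively.
- Keep the approach "with CMR tagging, on a segment-based approach" and account for segments within patients, for example by a mixed model with a patient random effect.
- Write out End-Point 1's contrasts. Normals enter with normal perfusion, so these are normal segments between groups, and abnormal segments of ischemic patients against the normal group.
- Name strain or rotation as the single primary measure in advance, or apply an adjustment such as Holm.
- State that selection on an LVEF drop affects the between-group change contrast, and that the within-patient class contrast of End-Point 2 is less exposed.

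**Cost.** No new imaging is needed, but a rest-only difference can no longer be claimed as a primary result. Power then depends on a rest-stress correlation the plan does not give. With 13 versus 22, 80% power needs a difference of 1.01 SD of the change. In single-state SDs this is 1.01 × √(2(1 − ρ)) = 1.19, 1.01, 0.78 or 0.45 at ρ = 0.3, 0.5, 0.7 or 0.9. Holm's first step over four tests (0.05/4 = 0.0125) raises 1.01 to 1.23. If d = 1.06 were in SDs of the change, power would fall from 0.84 to 0.65 at that step. Naming one measure costs less power than adjusting over both; if Holm is chosen, the sample size should be revisited.

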Volumetric data and late gadolinium enhancement post-processing will be performed on an AW workstation using ReportCard v4 software (General Electric). Tagged images will be post-processed for strain and displacement (ΔR and $\Delta\theta$) measurements using the HARP® tagging analysis software package (Diagnosoft) or a similar industry standard software package.

Primary End-Point Analysis:

For each patient group, every segment of the myocardium will be classified as normal, reversible, or non-reversible based on the PET perfusion data. Then for each segment category the radial strain (ΔR) and rotational displacement ($\Delta\theta$) will be calculated using the HARP® software package (Diagnosoft). These values will be determined from tagged cine images obtained in three short axis (apical, mid, and basal) views of the left ventricle obtained during regadenoson induced stress and rest (or difference in stress values). Comparisons will be made using ANOVA and standard t-test methods.

1. For Primary End-Point 1 we will compare the radial strain (ΔR) and rotational displacement ($\Delta\theta$) of normal and abnormal segments *between the defined ischemic and normal patient groups*.
2. For Primary End-Point 2 we will compare radial strain (ΔR) and rotational displacement ($\Delta\theta$) at rest and stress *between abnormal and normal segment classifications*.

Secondary End-Point 1

The secondary end-points of this study will be analyzed using regression analysis to determine the relationships between radial strain (ΔR), rotational displacement ($\Delta\theta$), regional flow reserve, and the degree of transmurality (TEI) as defined by the presence of delayed gadolinium enhancement.

Secondary End-Point 2

Adverse events will be recorded on an Adverse Event log. This log will track:

1. Description of event
2. Start and stop time of event
3. Severity of event
4. Likelihood that the event is related to the study drug
5. Relationship of event to other test procedures
6. Any treatment actions taken
7. The final outcome

Although serious adverse events are not expected, serious adverse events will be reported to the IRB.

Powering Calculation

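### Because controls have normal PET perfusion, abnormal segments come essentially only from ischemic patients: End-Point 1 is like-for-like only for normal segments, and End-Point 2 does not say whose normal segments are its reference

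*Combined protocol and SAP*

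**What the plan says.** - **Segment classes.** Under DATA ANALYSIS, Primary End-Point Analysis, "every segment of the myocardium will be classified as normal, reversible, or non-reversible based on the PET perfusion data". PRIMARY END-POINTS gives the same rule.
- **Cohorts.** STUDY PROCEDURES states that "15 subjects will be recruited who had normal perfusion, normal LVEF and no WMA on a clinically indicated cardiac PET study". Ischemic Patient Population selects the other 25 on a PET study "demonstrating reversible ischemic perfusion defect", together with a wall motion abnormality. A non-reversible defect is not required for entry.
- **End-Point 1** compares strain and displacement "of normal and abnormal segments between the defined ischemic and normal patient groups".
- **End-Point 2** looks for differences "between segment classifications (normal, reversible, and non-reversible perfusion defects"). Its analysis sentence says "between abnormal and normal segment classifications". Neither place says which cohort supplies the normal segments.
- **Outcome.** Values are those "obtained during regadenoson induced stress and rest (or difference in stress values"), so a rest-to-stress change is permitted.
- **Method.** "Comparisons will be made using ANOVA and standard t-test methods". No patient or cohort term is given.
- **Planned difference.** Powering Calculation expects the cohorts to differ by a net 10% in ejection-fraction change. It converts this to a 5.6% radius change and a Cohen's d of 1.06, with 13 normal and 22 abnormal evaluable patients.

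**The concern.** The PET perfusion result that assigns a patient to a cohort also assigns each segment to a class, so class and cohort are tied together by design. A control could still have an isolated segment classed abnormal, since no segment-level threshold is given, but the enrolment rule leaves little room for it.

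This has two consequences. End-Point 1 promises a between-cohort comparison of abnormal segments, for which controls have essentially no counterpart. End-Point 2 can be read in three ways: the reference may be the ischemic patients' own normal segments (a within-patient contrast), the control segments (a between-patient contrast), or both pooled.

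The study wants to relate local mechanics to local perfusion. If segments are pooled and the cohorts differ in general, part of that difference is reported as an effect of the local defect, and a positive End-Point 2 would not by itself show that strain follows the defect. The comparison of reversible with non-reversible segments lies essentially within the ischemic cohort and is not affected.

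**Working it through.** **Inputs from the plan (Powering Calculation).** 13 and 22 evaluable patients; d = 1.06; power 0.8.

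**Assumptions not in the plan.** 16 segments per patient; k = 2 to 10 abnormal segments per ischemic patient; none in controls; total segment SD of 1; within-patient correlation (ICC) of 0 to 0.5; two-sided 5% tests; no true class effect.

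**1. The plan's own figure.** 5.6/5.3 = 1.057, close to the stated 1.06. A two-sample t-test with d = 1.06 and power 0.8 needs 15 patients per group (16 stated). With 13 and 22 its power is 0.84 (0.8 stated). The figures are near enough to use, but they describe a comparison of two patient groups on a radius change derived from ejection fraction, not a comparison of segment classes.

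**2. Control share of normal segments if pooled.** Share = 13×16 / [13×16 + 22×(16 − k)].

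| k | Control normal segments | Ischemic normal segments | Share |
|---|---|---|---|
| 2 | 208 | 308 | 40% |
| 5 | 208 | 242 | 46% |
| 10 | 208 | 132 | 61% |

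If all segments of ischemic patients are shifted by s relative to controls, the pooled normal mean moves by only part of s. The normal-versus-abnormal contrast then shows share × s with no class effect at all.

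**3. Size at ICC 0, k = 5.** Applying d to patient means, s = 1.06 × √(1/16) = 0.265 segment SD. The bias is 0.462 × 0.265 = 0.122 SD. With 208 + 242 = 450 normal and 22 × 5 = 110 abnormal segments, SE = √(1/450 + 1/110) = 0.106. The ratio is 1.15, so the rejection probability is about P(Z > 1.96 − 1.15) + P(Z < −1.96 − 1.15) = 21%. Simulation gives 20%.

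| Common shift, as a fraction of d = 1.06 | 0 | 1/4 | 1/2 | 1 |
|---|---|---|---|---|
| Pooled t-test, ICC 0 | 4–5% | 5–7% | 9% | 20% |
| Pooled t-test, ICC 0.3 | 10% | 14–15% | 30% | 72% |
| Pooled t-test, ICC 0.5 | 12–13% | 20% | 41% | 85% |
| Within-patient contrast, ischemic patients only | about 5% | about 5% | about 5% | about 5–6% |

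Ranges are across repeated simulations of 5,000 to 10,000 trials; the last row covers ICC 0, 0.3 and 0.5.

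**4. What the rows mean.** The ICC 0 row isolates the reference problem. The rows at ICC 0.3 and 0.5 exceed 5% even with no shift, because a t-test on segments ignores clustering; that is a separate error. Only the full-shift column agrees with both d = 1.06 and no class effect. If the cohorts differ by 1.06 but normal segments carry only part of it, the rest sits in abnormal segments and is a real class effect.

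**The case against.** **No section says that segments are pooled across cohorts.** The analysis text opens by referring to each patient group, and it separates the between-group contrast from the between-class contrast. This stands, and it makes the bias conditional. It does not settle the reference. The opening phrase governs classification, and if it also governed End-Point 2, that analysis would in effect be confined to ischemic patients, which the plan should then say.

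**End-Point 1 can be run.** The HYPOTHESIS section speaks of comparing normal, ischemic and infarcted myocardium with low-likelihood normals. On that reading, each kind of ischemic-patient segment is compared with control segments. This stands: a reader might infer that End-Point 1 is void, and the documents do not support that. What is missing is a statement that the abnormal-segment contrast combines class and cohort.

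**A rest-to-stress change removes stable patient differences.** This is partly right and may shrink the bias. It need not remove it, because the difference planned for in Powering Calculation is itself a difference in rest-to-stress change. The plan does not say how much of it normally perfused segments share.

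**The effect size is borrowed.** d = 1.06 rests on ejection fraction and the spread of normal resting values, not on segment strain or rotation. This stands; the percentages are illustrations.

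**Three classes against two.** The analysis sentence names only abnormal and normal, but the same section repeats the three classes and names ANOVA, so abnormal may be shorthand. This is not a contradiction to press.

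**Conclusion.** The point holds as an ambiguity in two primary end-points with a conditional bias. From the text alone, abnormal segments come essentially only from ischemic patients, End-Point 1 is like-for-like only for normal segments, End-Point 2 names no reference, and the stated methods have no patient or cohort term.

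If segments are pooled, 40% to 61% of any cohort shift enters the class contrast. At ICC 0 with 5 abnormal segments per ischemic patient, a nominal 5% test rejects about 20% under the full planned shift and about 5% to 9% under half of it or less. These figures rest on the assumed segment counts and on carrying d = 1.06 over to segment measures.

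A reader might infer that End-Point 2 as planned has a false-positive rate of 72% or 85%. The documents do not support that. Those figures need pooling, the full shift and an ICC of 0.3 or 0.5, and they include the separate clustering error. Confidence is high for the ambiguity and lower for the size of any bias. It should be fixed before analysis.

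**What to change.** **End-Point 1.** State two contrasts: (a) PET-normal segments in ischemic patients against segments in normal patients; (b) PET-abnormal segments in ischemic patients against segments in normal patients. Note that (b) combines class and cohort effects.

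**End-Point 2.** State it as a within-patient class contrast in ischemic patients, with the three classes of PRIMARY END-POINTS. Replace plain ANOVA and t-tests by a model with patient fixed effects. A patient random effect is an alternative if the model also includes cohort and each patient's fraction of abnormal segments. Without that fraction, a random intercept draws on between-patient information: in a deliberately extreme check, where defect extent followed patient-level function, it rejected about 8% of the time (only 300 trials, so imprecise). Adjusting for segment location is an optional refinement.

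**Cost.** Rewording two end-point definitions and two analysis sentences, and slightly more analysis work. There are no new data, and the 40 subjects stay as they are.

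**Precision.** With k = 5 in 22 patients, the class contrast has SE = √[(1 − ICC)(1/5 + 1/11)/22], so the difference detectable with 80% power (about 2.8 SE) is 0.32 SD at ICC 0 and 0.23 SD at ICC 0.5. The non-reversible class may be much less precise, because entry does not require such a defect. If 8 patients had 2 such segments each (an assumption), the same formula with (1/2 + 1/11)/8 gives about 0.76 and 0.54 SD against normal segments. The plan should state this limit.
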